6.2.13 Change from Baseline

Change from baseline in absolute terms is defined as the baseline value subtracted from the post-baseline values. This calculation method will be used as part of the calculation for percentage change from baseline calculations.

$$\text{Change from Baseline} = \text{Post-baseline Value} - \text{Baseline Value}$$

6.2.14 Percent Change from Baseline

Percent change from baseline will be calculated as change from baseline multiplied by 100 then divided by the baseline value.

$$\text{Percent Change from Baseline} = \frac{\text{Change from Baseline} \times 100}{\text{Baseline Value}}$$

6.2.15 Duration of Fibromyalgia

Duration of fibromyalgia at baseline (in years) will be calculated as date of first dose – onset date + 1 / 365.25. Onset date of fibromyalgia will be taken as reported on the medical history form.

6.2.16 Pooled Sites

The study protocol indicates that study site will be included as factor in statistical models. It was further indicated that the study can include up to 52 study sites in the United States. It is likely that some of these sites will have small numbers of subjects included in the mITT population, which could lead to convergence issues, unreliable treatment effect estimates and p-values. Thus, in the event that there are study sites with fewer than 6 subjects included in the mITT population, these sites will be pooled together to form a single site, such that the pooled sites will have a minimum of 6 subjects included in the mITT. The resulting pooled sites (referred to as “site” from here on) will be used in the analyses.

6.2.17 Numerical Rating Scale

The Numerical Rating Scale (NRS) is a unidimensional, segmented numeric scale in which a respondent selects a whole number (0-10 integers) that best reflects the intensity of the pain. The format is a horizontal bar or line that is anchored by terms describing pain levels where a score of 0 represents “no pain” and a score of 10 represents “worst pain imaginable”. Subjects will report average pain intensity related to fibromyalgia in the past 24 hours daily (from 4am to 4am of subsequent day) at bedtime in the handheld diary.

6.2.17.1 Baseline Mean NRS Score

The baseline mean NRS score is defined as the average of the NRS scores on the last 7 days prior to the first dose of study drug (Study days -7 to -1). A minimum of 5 non-missing NRS scores out of the 7 days is required for the baseline mean NRS score.

Baseline NRS = Sum of daily NRS scores (over 7 days)/ Number of available diaries

6.2.17.2 Post-Baseline Weekly Mean NRS Scores

Weekly Mean NRS Scores for Week 12 (and prior weeks) will be obtained based on the subject’s actual Week 12 visit date. If the subject’s Week 12 visit date is within Day 80 to Day 88, then the 7th NRS score for Week 12 will be the corresponding NRS score on the day before the subject’s Week 12 visit date, and the 6th to 1st NRS score for Week 12 will be obtained backwards from this. Thus, the corresponding NRS scores on the last 7 days prior to Week 12 actual visit date will be used for Week 12. Consequently, the Week 11 NRS scores will be obtained by counting 7 days backwards from the 1st NRS score for Week 12, Week 10 NRS scores will be obtained by counting 7 days backwards from the 1st NRS score for Week 11 and continuing up to Week 1. If the subject’s

actual Week 12 visit date is beyond Day 88, then the corresponding NRS score on the day before Day 88 (i.e., Day 87) will be used as the 7th NRS score for Week 12, and the 6th to 1st NRS score will be obtained backwards from this and continuing for each week from Week 11 to Week 1. Meanwhile, if the subject's actual Week 12 visit date is earlier than Day 80, then no Week 12 data will be identified.

Timing of Week 12 Visit	Reference Day (NRS)
Day 80 to Day 88	Count backwards from day before Week 12 visit (Week 12 study day -1)
Day 89+	Count backwards from Day 87 only
Earlier than Day 80	No Week 12 data identified

For subjects that withdraw early or have missing data such that they do not have any data that would fall into the Week 12 windowing, their last non-missing diary day will serve as the anchor; weeks will be counted backwards in 7-day intervals from the last day. For the week ending with this anchor day, study week will be assigned such that the majority of days fall in the nominal week. For example, Week 11 is nominally day 71-77; if a subject's last value is on day 74, the majority of the resulting 7-day window working backwards would be in "Week 11", so their last week would be analyzed as "Week 11" and the subsequent intervals assigned descending weeks working backwards. The following table shows how the last interval will be assigned based on its last day.

Timing of Last Non-Missing Diary	Assigned Week (from which to count backwards)
Day 1 to Day 10	Week 1
Day 11 to Day 17	Week 2
Day 18 to Day 24	Week 3
Day 25 to Day 31	Week 4
Day 32 to Day 38	Week 5
Day 39 to Day 45	Week 6
Day 46 to Day 52	Week 7
Day 53 to Day 59	Week 8
Day 60 to Day 66	Week 9

Timing of Last Non-Missing Diary	Assigned Week (from which to count backwards)
Day 67 to Day 73	Week 10
Day 74 to Day 80	Week 11
NA	Week 12

Change from baseline and percent change from baseline will be calculated by subtracting baseline mean score from the post-baseline weekly mean scores, as defined in Sections [6.2.13](#) and [6.2.14](#).

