pain scores from the handheld devices to determine randomization eligibility. Subjects whose mean of the daily average pain intensity score during the preceding seven (7) days is within the protocol-defined algorithm and whose compliance with daily diary completion is found to be adequate will be eligible for randomization. The absolute pain scores and variability among scores, as well as the actual percentage required for diary compliance, will be masked to investigators and subjects. Subject eligibility for randomization into the study based on these variables will be communicated to the investigator via the IRT system. The IRT system will notify the site if the subject is "Eligible" or "Not eligible." No other information will be provided.

Eligible subjects will be randomized to receive either oral NYX-2925 50 mg, NYX-2925 100 mg or placebo daily for 12 weeks. Investigators and subjects will be both blinded to treatment allocation and masked to the randomization criteria.

Subjects will be dispensed a four-week supply of study drug and instructed to take one (1) capsule by mouth once daily. The first dose of study drug will be taken in the clinic during Visit 2 (Week 0). Subjects will be instructed to take study medication one time per day throughout the study. Acetaminophen will be dispensed/re-dispensed for use as rescue medication for pain related to fibromyalgia; instructions to take no more than 3 g/day (one to two 500 mg tablets every 6 hours as needed) will be reinforced.

Adverse event collection will begin from the time of study drug administration through the last day of the subject's participation in the study.

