Study Period	Screening		Baseline		Treatment Period		
	Study Week	1 to 4 weeks ^a (-28 to -1)	Week 0 ^d (1 ±2)	Week 2 (14 ±2)	Week 4 (28 ±4)	Week 8 (56 ±4)	Week 12 ^b (84 ±4)
Study Visit	Visit 1	Visit 2	Visit 3 ^v	Visit 4	Visit 5	Visit 6	
Record average pain intensity ^m and rescue medication use over past 24 hours at bedtime for each day	X	X	X	X	X	X	X
Randomize eligible subjects		X					
Dispense study drug ^o		X					
Confirm subject takes first dose of study drug (in the clinic)		X					
Confirm study drug dosing each day via handheld device		X	X	X	X	X	X
Return study drug and assess compliance ^l			X	X	X	X	X
Misuse, Abuse, and Diversion Drug Event Reporting System [®] (MADDERS) ^s				X	X	X	X
Record Daily Sleep Interference Scale (DSIS) each morning ⁿ	X	X	X	X	X	X	X
Assess handheld diary compliance		X	X	X	X	X	X
MINI International Neuropsychiatric Interview (MINI)	X		X	X	X	X	X
Fibromyalgia Impact Questionnaire – Revised (FIQR)				X	X	X	X
Patient Reported Outcomes Measurement Information System – Fibromyalgia (PROMIS _{TM}) ^t			X	X	X	X	X
Patient Global Impression of Change (PGI-C) scale					X	X	X
Sheehan Suicidality Tracking Scale (S-STS)	X	X	X ^v	X	X	X	X
Concomitant medications ^q	X	X	X	X	X	X	X
Adverse events ^r	X	X	X	X	X	X	X
Safety follow-up calls							X ^y

^a Subjects will discontinue all concomitant analgesic medications taken for pain related to fibromyalgia. Duration of the period will depend upon the analgesic(s) being discontinued, not to exceed 4 weeks. Subjects not taking any concomitant analgesic medications at Visit 1 may directly begin Week -1 of the Screening Period.

^b ET=Early Termination. Subjects who prematurely discontinue randomized treatment will have Week 12 procedures performed. Diary completion ends the night before the Week 12 visit.

^c Informed consent includes an additional consent for inclusion in a secure, proprietary, research subject database to screen for protocol violators. The main informed consent document may be executed up to 30 days prior to the screening visit. The date the first screening related activity is completed will be considered the subject's screening date. If the subject does not complete the screening visit within 30 days of signing the informed consent document, the subject must be reconsented.

^d Verify subject still meets all inclusion criteria and does not meet any exclusion criteria.

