6.2.3 Duration / Study Day / Time

Study day will be calculated as the number of days from first dose of study drug.

- date of event – date of first dose of study drug + 1, for events on or after first dose
- date of event – date of first dose of study drug, for events before first dose

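### SAP 6.2.17.2 counts diary weeks backwards with no stop at first dose, so as written Week 1 pain means take in 5 to 1 baseline days for Week 12 visits on Days 80 to 84

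*SAP*

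**What the plan says.** SAP 6.2.17.2 fixes the Week 12 NRS window by the actual visit. For a visit on Days 80 to 88 the instruction is "Count backwards from day before Week 12 visit (Week 12 study day -1"). Week 12 is the seven days ending there, and earlier weeks follow in contiguous blocks, with Week 10 found by "counting 7 days backwards from the 1st NRS score for Week 11 and continuing up to Week 1". Visits from Day 89 are anchored on Day 87. Visits before Day 80 give no Week 12 value. For subjects without Week 12 data, "their last non-missing diary day will serve as the anchor; weeks will be counted backwards in 7-day intervals from the last day", and a table assigns the last block to a week.

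Baseline (SAP 6.2.17.1) is the "average of the NRS scores on the last 7 days prior to the first dose of study drug (Study days -7 to -1"). A completeness rule is given there: "A minimum of 5 non-missing NRS scores out of the 7 days is required for the baseline mean NRS score". No minimum is stated for any post-baseline week.

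Under SAP 6.2.3 the first dose date is Day 1. Earlier dates are numbered as the event date minus the "date of first dose of study drug, for events before first dose", so there is no Day 0. The protocol synopsis says "The first dose of study drug will be taken in the clinic during Visit 2 (Week 0"). Protocol Table 3 sets the Week 12 visit at Day 84 ±4, and its footnote b says "Diary completion ends the night before the Week 12 visit".

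DSIS weeks (SAP 6.2.18) count from the visit day itself. The DSIS reference-day table is labelled as covering rescue medication too, whereas SAP 6.2.19 sends rescue weeks to the NRS method.

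**The concern.** Baseline and Week 1 should not share diary entries. Where they do, the same scores enter both sides of the Week 1 change from baseline. The number shared depends on when the final visit was booked, some eleven weeks later, and not on anything that happened in Week 1.

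Week 1 change is part of a listed secondary endpoint (SAP 3.2, NRS change at each week from Week 1 through Week 12). SAP 6.11.2 reports it with a confidence interval and p-value, and it is the first point of the line plot. Rescue tablets are summed by week (SAP 6.2.19), so a Week 1 total could include tablets taken in screening.

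**Working it through.** **The plan's own example.** A last diary on Day 74 gives a block of Days 68-74. Four of its seven days (71-74) lie in nominal Week 11 (Days 71-77), so the SAP assigns Week 11. This reproduces. The same majority rule reproduces the assignment table for every last-diary day from 4 to 80.

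**NRS, subjects with a Week 12 visit.** For a visit on Day V (80 to 88), Week 12 ends on Day V - 1. Week 1 ends 7 × 11 = 77 days earlier, on Day V - 78. Pre-dose days in Week 1 = max(0, 7 - (V - 78)) = max(0, 85 - V).

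| V | Week 1 days | Pre-dose days | Share of mean, full diaries |
|---|---|---|---|
| 80 | -5 to -1, 1-2 | 5 | 5/7 = 71% |
| 81 | -4 to -1, 1-3 | 4 | 57% |
| 82 | -3 to -1, 1-4 | 3 | 43% |
| 83 | -2, -1, 1-5 | 2 | 29% |
| 84 | -1, 1-6 | 1 | 14% |
| 85 | 1-7 | 0 | 0 |
| 88, and 89+ | 4-10 | 0 | 0 |

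Every pre-dose day lies within Days -7 to -1. Week 2 starts on Day V - 77, so no earlier than Day 3. Week 12 starts on Day V - 7, so no earlier than Day 73. Only Week 1 is touched.

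**NRS, early terminators.** With last diary on Day D assigned to Week w, Week 1 ends on Day D - 7(w - 1). Last diaries on Days 1-6 give 6 to 1 pre-dose days. From Day 11, the first three days of each table row give 3, 2, 1. That is 6 + 10 × 3 = 36 of 80 possible last-diary days.

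**DSIS and rescue.** Counting from the visit day gives max(0, 84 - V) entries with negative study days: 4, 3, 2, 1, 0 for V = 80 to 84. Any waking entry on Day 1 would also precede the in-clinic first dose. Rescue weeks hold 5 to 1 pre-dose days by the NRS method, or 4 to 0 from the visit day.

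**Dilution of the Week 1 change.** This needs assumptions on effect shape and visit days, which the documents do not give.

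- Constant effect from Day 1: dilution equals the share in the table. With visits uniform over Days 80-88 the average is (5+4+3+2+1)/(9 × 7) = 15/63 = 23.8%. With all visits on Day 84 it is 14.3%.
- Linear build-up over Days 1-7, then a plateau: the true Week 1 total is proportional to 1+...+7 = 28. V = 80 gives 1 - 3/28 = 89%; V = 84 gives 1 - 21/28 = 25%; V = 88 gives 1 - 43/28 = -54%, an inflation because Week 1 then starts on Day 4. The uniform average is 21.0%. Stopping the count at Day 1 lowers it to 8.1%.

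**Reach to Week 12.** Week 1 enters the primary MMRM only as one of twelve repeated measures. A simulation took 85 per arm, SD 1.7 and difference 0.73 from SAP Section 4. All else was assumed: placebo change -1.5; linear rise to a plateau at Week 4; correlation 0.6 compound-symmetric or 0.9 AR(1); dropout 10, 20 or 30%; visits uniform on Days 80-88, uniform on Days 80-84, or all on Day 84; 400 trials per setting; no site or baseline terms. The mean shift in the Week 12 contrast was at most 0.004 points, and the largest single-trial shift was 0.07. A repeat that diluted dropouts by the early-terminator rule again gave a mean shift of at most 0.004. Its most extreme single trial moved by 0.11, in the harshest setting (30% dropout, all visits on Days 80-84). For scale, the standard error of a two-arm difference is 1.7 × √(2/85) = 0.26.

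**The case against.** The best reply is that the SAP leaves a stop unstated and does not intend to use pre-dose scores. The section heading says post-baseline. Days -7 to -1 are assigned to baseline. Week 11 is nominally Days 71-77, which makes Week 1 Days 1-7. The assignment table places last diaries on Days 1-3 in Week 1, although most of an untruncated block would then be pre-dose; that fits a window cut at first dose. Dataset specifications sit in a separate document (SAP 6.3.2) and may hold a filter, and parts of the public SAP are redacted.

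This stands as evidence of intent. It does not supply a rule: a programmer who follows 6.2.17.2 literally gets the counts above, and none of the eight changes in the post-lock addendum touches that section. It does mean that nobody can say from these documents that the reported Week 1 values contain pre-dose days.

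The reply is also right that the consequence is small. One of twelve weeks in one secondary endpoint is affected. In a double-blind trial there is no stated reason for completers' visit days to differ by arm, so the mixing would weaken a Week 1 difference and not create one. A reader might infer a false-positive risk from the absence of multiplicity control on secondary endpoints (SAP 6.11.6); the documents do not support that. Nor is 36 of 80 a share of subjects: it counts calendar days.

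**Conclusion.** The rule is wrong as written, for Week 1 only. The day counts (5, 4, 3, 2, 1 for visits on Days 80 to 84, then 0) follow from the SAP's text and day numbering without further assumption, and they include the protocol's target visit day. The shares of 71 to 14% assume complete diaries. The average dilution depends on an unknown visit-day distribution and effect shape, so the 14 to 25% range in the examples is illustrative.

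A reader might go further and infer that the primary Week 12 result is contaminated. It is not: no Week 12 window contains a pre-dose day, and the indirect effect through the MMRM averages at most 0.004 points against an assumed difference of 0.73, under the simulation's assumptions. The point merits correction because it is cheap to settle and decides whether the Week 1 estimate can be read as on-treatment data.

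**What to change.** Add to SAP 6.2.17.2 that post-baseline weekly NRS means use only entries with Study Day 1 or later, and show the number of contributing Week 1 days. Check the dataset specifications and programs first. If they already exclude pre-dose days, stating so is enough. If pre-dose days were used, rerun the Week 1 outputs and the MMRM, labelled as a post-lock correction, since the addendum records that the study was already unblinded.

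For DSIS, exclude entries with negative study days and state how a Day 1 waking entry is treated: it precedes the first dose but falls outside the Day -7 to -1 baseline, so dropping it would leave it in neither period.

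For rescue medication, reconcile the two anchors in 6.2.18 and 6.2.19, which is a separate conflict, and exclude pre-dose days. Analyse tablets and mg as a mean per available diary day (or that mean times 7) for all subjects and weeks. A stop at Day 1 applied to a raw sum would report, under the NRS method, a 2- to 6-day total as a weekly amount for visits on Days 80 to 84.

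The cost is a few sentences, one filter, a changed rescue summary and possibly a rerun. Week 1 NRS would rest on 2 to 6 days for visits on Days 80 to 84, and on 1 to 6 for affected early terminators, with no stated minimum; hence the day count. Weeks 2 to 12 NRS means do not change. Drift from visit-anchored weeks remains (8.1% in the linear example).

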6.2.17.3. Definition of $\geq 30\%$ and $\geq 50\%$ Responder

Subjects who achieve a percent reduction in NRS score relating to ‘Average pain intensity the past 24 hours’ of $\geq 30\%$ (programmatically, where the percent change from baseline value is ≤ -30) at Week 12 will be classified as responders, and non-responders otherwise.

Similarly, subjects who achieve a percent reduction in NRS score relating to ‘Average pain intensity in the past 24 hours’ of $\geq 50\%$ (programmatically, where the percent change from baseline value is ≤ -50) at Week 12 will be classified as responders, and non-responders otherwise.

Subjects with missing weekly mean NRS score relating to ‘Average pain intensity related to fibromyalgia in the past 24 hours’ at Week 12 will be classified as non-responders.

6.2.17.4

6.2.18 Daily Sleep Interference Scale

The Daily Sleep Interference Scale (DSIS) is a single-item measure with 11-point response scale (0-10; where 0 corresponds to “did not interfere with sleep” and 10 corresponds to “completely interfered with sleep/unable to sleep due to pain) that quantify sleep interference due to pain. The subjects complete this questionnaire daily upon awakening each morning.

Baseline mean score will be obtained as described in Section [6.2.2](#). Weekly mean DSIS data will be obtained for Week 12 data (and prior weeks) based on the subjects actual Week 12 visit date.

If the subject’s Week 12 visit date is within Day 80 to Day 88, then data on the actual Week 12 visit date up to 6 days prior to this date will be the corresponding data for Week 12 visit date. Consequently, the Week 11 data will be obtained by counting 7 days backwards from the 1st day of Week 12, Week 10 NRS scores will be obtained by counting 7 days backwards from the 1st day of Week 11, and the process continue up to Week 1. If the subject’s actual Week 12 visit date is beyond Day 88, then the corresponding data from Day 82 to Day 88, inclusive, will be the Week 12 data. Similar process as described previously will be used to obtain the data for each week from Week 11 up to Week 1. Meanwhile, if the subject’s actual Week 12 visit date is earlier than Day 80, then no Week 12 data will be identified.

Timing of Week 12 Visit	Reference Day (DSIS or Rescue Medication)
Day 80 to Day 88	Count backwards from day of Week 12 visit
Day 89+	Count backwards from Day 88 only
Earlier than Day 80	No Week 12 data identified

For subjects that withdraw early or have missing data such that they do not have any data that would fall into the Week 12 windowing, their last non-missing diary day will serve as the anchor, as described in Section [6.2.17.2](#).

6.2.19 Rescue Medication

Use of rescue medication (number of tablets taken) is recorded daily at bedtime in the handheld diary. Weeks will be identified and assigned using the same method as described in Section [6.2.17.2](#) for NRS data. For each week, the total number of tablets reported per week will be summed and percentage of rescue-free days per week will be obtained.

A subject using rescue medication is defined as any subject who recorded one or more tablets in the daily diary at any time after the first dose of study drug.

Percentage of rescue-free days per week will be obtained by taking the number of days where rescue medication was answered ‘No’ in the daily diary and divided by the number of non-missing diary entries for the week.

Weekly dosage of acetaminophen (mg) will be calculated using the total number of tablets taken for each week multiplied by 500 mg.

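### SAP 6.2.19 sums reported rescue tablets with no divisor, so weekly tablets and mg depend on diary completion, and Week 1 has no stated cut at the first dose

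*SAP*

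**What the plan says.** SAP 6.2.19 defines three kinds of rescue variable from the bedtime diary.

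- **Amount.** For each week "the total number of tablets reported per week will be summed and percentage of rescue-free days per week will be obtained". The dose follows from it: "Weekly dosage of acetaminophen (mg) will be calculated using the total number of tablets taken for each week multiplied by 500 mg". No divisor, minimum number of entries or rule for an incomplete week is stated.
- **Frequency.** The count of rescue-free days is "divided by the number of non-missing diary entries for the week".
- **Any use.** A user is a subject who "recorded one or more tablets in the daily diary at any time after the first dose of study drug".

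For the week limits, 6.2.19 says "Weeks will be identified and assigned using the same method as described in Section" 6.2.17.2, the NRS rule. That rule anchors Week 12 on the day before the Week 12 visit (Day 87 for visits after Day 88) and obtains the earlier weeks by "counting 7 days backwards from the 1st NRS score for Week 11 and continuing up to Week 1". For subjects without Week 12 data, "weeks will be counted backwards in 7-day intervals from the last day". Neither rule states a cut at Day 1. The table in 6.2.18, however, has a column headed "Reference Day (DSIS or Rescue Medication") and counts back from the visit day itself, or from Day 88.

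SAP 6.11.4.9 fits an MMRM to the weekly mg for Weeks 1 to 12 and reports a p-value for the treatment difference at each week. Tables 14.2.2.13.1 (one-sided) and 14.2.2.13.2 (two-sided) are titled as a weekly mean dose. The protocol synopsis planned only a descriptive summary of rescue use. The post-lock addendum does not change 6.2.19.

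**The concern.** A sum over reported entries measures two things at once: how much the subject took, and how many evenings the subject filled in the diary. The authors allowed for missing entries in the rescue-free-day percentage but not in the tablet and mg totals three sentences away. If one arm completes fewer diaries, its weekly mg falls with no difference in use, and the MMRM would report that as a treatment effect.

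The week limits add a second problem. Counting back in 7-day blocks from a variable end date need not land on Day 1. Where Week 1 reaches before the first dose, the SAP does not say whether those days count. Week 1 is then either a short, unscaled sum or a mixture of screening and on-treatment use. Two competent programmers could produce different values from the same diaries.

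**Working it through.** **Inputs.** Raw-sum and mg rules, rescue-free-day denominator and any-use limit: SAP 6.2.19. Week rules: SAP 6.2.17.2 and 6.2.18. No Day 0: SAP 6.2.3. Week 12 visit on Day 84±4, so Days 80 to 88, with diaries ending the night before: protocol Table 3 and footnote b. Rescue diary starting at Week -1: protocol synopsis. Maximum 6 tablets a day: SAP 1. The documents give no missing-day rate, so every rate below is an assumption.

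**Reproducing the SAP's own windows.** With Week 12 = anchor − 6 to anchor, an anchor of Day 88 gives Days 82 to 88, as 6.2.18 states. Assigning the last week by majority of days gives Day 1–10 = Week 1, Day 11–17 = Week 2, and so on to Day 74–80 = Week 11, which matches the 6.2.17.2 table.

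**1. Missed days.** With u tablets a day and m missed days, the raw sum is u(7 − m), a loss of m/7: 14.3% for 1 day, 28.6% for 2, 42.9% for 3. At an assumed 3 tablets a day:

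- complete week: 21 tablets, 10,500 mg;
- 1 day missed: 18 tablets, 9,000 mg;
- 2 days missed: 15 tablets, 7,500 mg.

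*Unequal completion, equal true use.* False difference = gap/7 of the full weekly total: 3.6%, 7.1% or 14.3% for a gap of 0.25, 0.5 or 1 day per week. In mg, 10% against 20% of days missed gives u × 7 × 500 × 0.10 = 350, 1,050 or 2,100 mg per week at 1, 3 or 6 tablets a day.

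*Equal completion.* If every subject loses the same fraction f, all values are multiplied by (1 − f). The estimated difference shrinks by f = 7.1%, 14.3% or 28.6% for 0.5, 1 or 2 days per week. The standard error shrinks by the same factor, so their ratio does not move.

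**2. Week 1 under the NRS rule.** For a visit on Day V (80 to 88), Week 12 ends on Day V − 1, and Week 1 ends 77 days earlier, on Day V − 78. On-treatment days in Week 1 = min(7, V − 78).

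| Visit day | Pre-dose days | On-treatment days | Share of week covered if pre-dose days are dropped | Share that is pre-dose if they are kept |
|---|---|---|---|---|
| 80 | 5 | 2 | 29% | 71% |
| 81 | 4 | 3 | 43% | 57% |
| 82 | 3 | 4 | 57% | 43% |
| 83 | 2 | 5 | 71% | 29% |
| 84 | 1 | 6 | 86% | 14% |
| 85–88 | 0 | 7 | 100% | 0% |

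Visits after Day 88 give Week 1 = Days 4 to 10, with no pre-dose days. So 5 of the 9 days in the visit window, including the nominal Day 84, put pre-dose days into Week 1.

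For early withdrawals with a last diary on Day D assigned to Week k, Week 1 ends on Day D − 7(k − 1). For k = 1 and D = 1 to 6, it holds 6 to 1 pre-dose days. For k = 2 to 11 and D = 7k − 3, 7k − 2 or 7k − 1 (Day 11–13, 18–20, … 74–76), it holds 3, 2 or 1.

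**3. The 6.2.18 header.** If it were followed, Week 12 would be Days V − 6 to V. The last bedtime entry is on Day V − 1, so visits on Day 80 to 88 would have at most 6 of 7 entries. Under 6.2.17.2 all 7 are possible.

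**4. Number of tests.** 12 weeks × 2 doses = 24 contrasts; two tables, one-sided and two-sided, make up to 48 p-values.

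**The case against.** The SAP never says that a missed day counts as zero. It sums what is reported, and the table titles suggest that an average was intended. Dataset specifications and table shells are separate documents (SAP 6.3.2 and 6.3.6), and an averaging rule could stand there. This is fair: the zero contribution is what the text yields when followed literally, not something it declares. But the SAP is where the derivation is defined, and it derives no mean.

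On Week 1, the heading of 6.2.17.2 speaks of post-baseline scores, and SAP 6.2.2 and 6.2.17.1 assign Days -7 to -1 to baseline. Together these favour leaving pre-dose days out. That is the better reading, but no cut is stated, and under a raw sum leaving them out gives an unscaled total over 2 to 6 days for visits on Day 80 to 84.

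The header conflict is largely editorial, since 6.2.19 expressly sends rescue medication to the NRS rule. A reader might infer that Week 12 rescue data lose a day; that follows only if the header overrides 6.2.19, and nothing says it does.

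Missed entries can be seen through diary review at visits and through the listings of daily rescue use (16.2.6.2) and of tablets dispensed and returned (16.2.5.4). None of these enters the weekly sum.

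A reader might also infer that missed days always weaken the test. They do not when the missed fraction is uniform.

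**Conclusion.** The derivation should be corrected. As written, weekly tablets and mg depend on diary completion, at 1/7 of the week per missed day under constant use. The risk to inference is unequal completion between arms, which can bias the weekly mg contrasts in either direction. The percentages above rest on assumed missing-day rates and on missed days resembling completed ones; the actual size is unknown. The Week 1 counts are exact consequences of the stated rules.

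The scope is limited to one secondary endpoint without multiplicity control. The missed-day problem affects the amount component. The pre-dose days affect both the weekly sums and the rescue-free-day percentage, because dividing by non-missing entries does not remove pre-dose entries. The proportion of subjects using rescue is untouched: it is limited to entries after the first dose and does not use weeks.

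A reader might infer that the primary result is in doubt. The documents do not support that. No rescue variable enters the primary model, and although the same back-counting sets the NRS weeks, the primary contrast is at Week 12, whose window holds no pre-dose days.

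**What to change.** - Define weekly tablets as 7 × (tablets reported ÷ on-treatment days with a non-missing rescue entry), and weekly mg as that × 500. At the assumed 3 tablets a day this stays at 21 tablets and 10,500 mg whether 0, 1 or 2 days are missed.
- Exclude pre-dose days from weekly tablets, weekly mg and the rescue-free-day percentage, in line with the any-use rule in the same section.
- Remove the reference to rescue medication from the 6.2.18 column header, leaving 6.2.17.2 as the only window.
- State whether a minimum number of entries applies. This is the sponsor's choice. The 5-of-7 rule in 6.2.17.1 is written for baseline NRS only; the SAP sets none for post-baseline weeks, and applying 5 here would lose Week 1 for visits on Day 80 to 82.
- Because the addendum records that the study is already unblinded, report this as a supplementary analysis beside the planned one, not in its place.

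The cost is one derivation change, one header edit and extra output from data already collected. The downsides are that scaling assumes missed days resemble completed days, so it would overstate use if subjects skip the diary on days without rescue, and that weeks with few entries become noisier.
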